#### Page **46** of **66**

Sponsor:	ObsEva			
Protocol:	19-OBE2109-005			
Document Version No.:	1.0	Document Date:	18-MAY-2021	

The following C-SSRS data will be summarized by time point (baseline "Lifetime" or Prior to Study Entry, "Since Study Start" and each post-baseline time point):

The number of subjects experiencing the following, at any time post-baseline in the extension study, will be summarized from Month 6 up to Month 12.

- Any suicidal ideation or behavior
- Emergence of suicidal ideation.
- Worsening of suicidal ideation.
- Emergence of suicidal behavior.

Any suicidal ideation or behavior is defined as an answer "Yes" for at least one of five questions for suicidal ideation or for at least one of five questions for suicidal behavior.

Emergence of suicidal ideation/behavior is defined as having no suicidal ideation/behavior at baseline and having reported any type of suicidal ideation/behavior at any time post-baseline (including "Since Study Start" answers).

Worsening of suicidal ideation is defined to occur when the most severe suicidal ideation rating since study start at any time post-baseline is more severe than its rating at baseline. If data of suicidal ideation or behavior is missing at baseline then the subject will not be included in summaries of emergence or worsening of suicidal ideation or behavior. The "already enrolled subjects" C-SSRS version ("Prior to Entry Study") will be used as baseline for subjects already randomized at the time of protocol amendment 3 implementation.

Same analysis will be repeated on the extension follow-up period.

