## 4.8.10. Columbia-Suicide Severity Rating Scale (C-SSRS)

The C-SSRS questionnaire prospectively assess the occurrence of treatment-emergent suicidal ideation and behavior.

Subjects completed:

- either the "Baseline" C-SSRS version, capturing lifetime history of suicidal ideation and behavior, for subjects who were still in screening period in the main study,

- or the "already enrolled subjects" C-SSRS version, for subjects already enrolled in the Extension study, and who were providing answers to the C-SSRS for the first time during the study

- the "since last study visit" C-SSRS version, dedicated to subjects for whom the C-SSRS was completed at the previous study visit, for use at all remaining study visits.

The "Baseline" C-SSRS version was to be completed during Screening, or at Day 1 if not done during Screening.

CRS-BS-TP-000005 V 1.0

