- Table 14.4.12.2 Endometrial Biopsy Diagnosis by Classification and Primary Diagnosis from Month 12 up to Month 6 Extension Follow-up – Extension Safety Analysis Set
- Table 14.4.13.1 Concomitant Medications From Month 6 to Month 12 Extension Safety Analysis Set
- Table 14.4.13.2 Concomitant Medications From Month 12 to Month 6 Extension Follow-up– Follow-up Extension Safety Analysis Set
- Table 14.4.14.1 Transvaginal Ultrasound: Uterus Length, Width, Depth, uterine Volume and
- Thickness by Visit from Month 9 up to Month 6 Extension Follow-up Extension Safety Analysis Set
- Table 14.4.14.2 Transvaginal Ultrasound: Ovaries assessment by Visit from Month 9 up to Month 6 Extension Follow-up Extension Safety Analysis Set
- Table 14.4.15.1 Suicide-related Treatment Emergent Events (C-SSRS) from Month 7 up to Month 12 Extension Safety Analysis Set
- Table 14.4.15.2 Suicide-related Events (C-SSRS) from Month 1 ExFU to Month 6 ExFU Follow-up Extension Safety Analysis Set

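### The only behaviour-specific C-SSRS row in the SAP cannot count a new suicidal act by a woman with past suicidal behaviour or a missing baseline

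*SAP*

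**What the plan says.** SAP 4.8.10 lists four counts for Month 6 to Month 12 and repeats them for the extension follow-up:

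1. Any ideation or behaviour, pooled: "Any suicidal ideation or behavior is defined as an answer 'Yes' for at least one of five questions for suicidal ideation"; a positive reply to any of the five behaviour items also qualifies.
2. Emergence of ideation.
3. Worsening of ideation: "Worsening of suicidal ideation is defined to occur when the most severe suicidal ideation rating since study start" at any later time exceeds the baseline rating.
4. "Emergence of suicidal behavior", the only row specific to behaviour.

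The emergence rule is "Emergence of suicidal ideation/behavior is defined as having no suicidal ideation/behavior at baseline and having reported any type of suicidal ideation/behavior" afterwards, with answers in the Since Study Start column included. The baseline time point is given as "baseline 'Lifetime' or Prior to Study Entry". The screening form is described as "capturing lifetime history of suicidal ideation and behavior". For women already randomised when the scale was introduced, the prior-to-entry answers on the already-enrolled form serve as baseline. Protocol Appendix R shows no look-back limit for those answers. A woman with missing baseline data is left out of the emergence and worsening summaries.

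SAP 7.2 (Appendix B) plans two C-SSRS tables: 14.4.15.1 for treatment, whose title begins "Suicide-related Treatment Emergent Events (C-SSRS", and 14.4.15.2 for follow-up. It also plans a subject-level listing, 16.2.9.13.

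**The concern.** Requiring a clean lifetime history takes repeat acts out of the only row that shows behaviour. The since-last-visit form (Protocol 10.4.10 and Appendix S) asks about the interval since the previous visit and records actual, interrupted and aborted attempts and preparatory acts separately. A positive answer on it is a new event whatever the woman's history. Under the SAP rule, the same answer is counted as behaviour for one woman and not for another.

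After early termination, SAP 1.2 directs the analysis to safety and says the summary tables will be the basis for the results sections of the study report. A zero for emergent behaviour in a table of treatment-emergent suicide-related events could be read as no suicidal behaviour on treatment. With few women enrolled, one act makes the difference between none and some.

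**Working it through.** The plan gives no figure for this point, so the check applies the four written rules to every possible profile.

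**Inputs (SAP 4.8.10).** Baseline ideation rating b, from 0 to 5; highest post-baseline ideation rating p, from 0 to 5; past behaviour yes or no; new behaviour yes or no. The rules are:
- Pooled row: p > 0, or new behaviour.
- Emergence of ideation: b = 0 and p > 0.
- Worsening of ideation: p > b.
- Emergence of behaviour: new behaviour and no past behaviour.

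**Step 1. New act, by history.** There are 6 × 6 = 36 combinations of b and p.

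| Profile | In behaviour row | In pooled row |
|---|---|---|
| No past behaviour, new act | 36 of 36 | 36 of 36 |
| Past behaviour, new act | 0 of 36 | 36 of 36 |

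**Step 2. Pooled row only.** With past behaviour, a new act reaches no other row when p ≤ b. The count is 1 + 2 + 3 + 4 + 5 + 6 = 21 of 36. In the other 15 the woman also enters an ideation row, but because of her ideation, not the act.

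**Step 3. Can the table show the act?** Take women with past behaviour and some post-baseline ideation (p ≥ 1): 6 × 5 = 30 profiles. In 30 of 30 all four rows are identical with and without the new act. In the remaining 6 (p = 0) the act moves only the pooled row.

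**Step 4. Missing baseline.** These women are outside rows 2 to 4. A new act is tabulated in the pooled row only, at all 6 values of p.

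**Step 5. Ideation.** Worsening requires a rating that "is more severe than its rating at baseline". With baseline worst level r of at least 1, emergence is impossible and 5 − r levels can trigger worsening: 4 if r = 1, 2 if r = 3, 0 if r = 5.

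**Step 6. Scale, as illustration only.** The documents give neither the prevalence of past behaviour nor the number actually enrolled. The planned maximum reproduces: 450 × 0.80 × 0.80 = 288. Assuming 1% to 10% with past behaviour, 2.88 to 28.8 of 288 women (about 3 to 29) could never enter the behaviour row. In an assumed cohort of 50 it would be 0.5 to 5.

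**Step 7. With an any-behaviour row regardless of history.** All 36 of 36 profiles in the second line of the table are counted as behaviour.

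**The case against.** There are four objections.

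*The act is reported elsewhere.* This stands. It counts in the pooled row and appears in Listing 16.2.9.13. Protocol 12.1.1 asks for any event after consent to go on an adverse event or serious adverse event form. If that is done and the event is treatment-emergent, it enters the table by system organ class and preferred term, and the serious-event listing if it meets a seriousness criterion. A reader might infer that an attempt could vanish from the report; the documents do not support that. These routes do not correct the behaviour row, however, and the adverse event route depends on separate reporting.

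*Section 4.8.10 may intend a by-time-point summary.* The sentence above the four counts announces C-SSRS data summarised by time point, including baseline, and ends in a colon with no item list of its own. Emergence and worsening cannot be summarised at baseline, so something else may have been meant, or lost when the PDF was read. It is therefore too strong to say that no behaviour count was ever intended. But no behaviour item is named, and Appendix B lists no such table.

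*The trial is small and descriptive.* SAP 4.8.2 leaves several categories of serious or related event to listings because of low numbers, no hypothesis tests are planned, and the C-SSRS is not named among the safety endpoints in Protocol 7.2 or SAP 2.5.3. This lowers the priority. It does not make a misleading zero acceptable in a table that will be produced anyway.

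*The since-last-visit form alone does not cover every woman.* Correct. For a woman whose first C-SSRS was the already-enrolled form, earlier on-study acts are only in its Since Study Start column. The SAP counts those answers, and a repair must too.

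**Conclusion.** The point holds at moderate priority. As written, the only behaviour-specific count takes in 0 of 36 profiles with both past and new behaviour, and it omits every woman with missing baseline data. Her new act is tabulated only where it cannot be told apart from ideation. This follows from the definitions and needs no prevalence assumption. It does assume that the four rows are the whole tabulated content, as Appendix B suggests, and that the emergence rule is applied separately to ideation and to behaviour. Applied jointly, it would exclude more women.

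A reader might go further and infer that the excluded women are those at highest risk, or that a known share of the cohort is affected. The documents give no risk by history, no prevalence and no final enrolment, so neither inference is supported. The figures in step 6 are illustrations.

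**What to change.** In SAP 4.8.10 and Tables 14.4.15.1 and 14.4.15.2:

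- Add a row for any post-baseline suicidal behaviour, by type (actual, interrupted or aborted attempt, preparatory acts), and a row for any post-baseline suicidal ideation, by highest level 1 to 5. Count both regardless of history and include women with missing baseline data.
- Draw both rows from the since-last-visit form and from the Since Study Start column of the already-enrolled form. Flag events known only from that column, because they may have occurred before the extension period.
- Show each row by history: yes, no, missing.
- Keep the emergence and worsening rows.
- Complete the by-time-point sentence by naming the items to be summarised.

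The cost is SAP wording and a few table rows; all the items are already collected and listed. The downside is that the new counts do not net out history, so they need the history split to be interpreted.

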10.2.1.1 Study visit: Month 6 (Day 169 ± 3 days)

After all Month 6 assessments pertaining to the main study have been made and the subject has been confirmed to be eligible to proceed in the extension study (see section 9.2), the subject will be requested to sign the extension-specific ICF that she was given at the Month 5 visit.

Note: inclusion in the extension study will not be postponed if the results of any Month 6 assessment are not available on the day of Month 6 visit. Subjects will be required to stop the treatment if the results obtained after enrollment meet the discontinuation criteria defined in Section 10.7.2.1.

After signature of the extension-specific ICF, the subject will be dispensed new treatment kits. The subject will take her daily dose of study medication at the study site from these newly dispensed kits. The exact time of dosing (hour/minute) will be recorded in eCRF.

In addition, the subject will:

• receive contraception counselling and will be given double barrier contraception (condoms with spermicide), if requested, to be used until 3 months after treatment end. If the subject is at risk for

acquiring HIV, she must be reminded to use double non-hormonal barrier contraception without spermicides (eg: condoms and diaphragms).

- be provided/prescribed a limited quantity (as per Investigator's judgement) of standard doses of permitted analgesics as rescue medication for EAP for the duration of the study.
- receive calcium 500 to 1000 mg and vitamin D 400 IU supplementation

Upon completion of the visit, the subject will be provided with emergency contact phone numbers and will be scheduled for her next visits.

10.2.1.2 Study visits: Month 7 (Day 197 -3/+2 days) and Month 8 (Day 225 ± 3 days)

The following tests and evaluations will be performed :

- eDiary completion compliance check
- ePRO and ClinRO completion, ideally before any other procedures or assessments:
 - at Month 7 visit: EHP-30, EQ-5D-5L, PROMIS, mPGIS, PGIC, HRUQ, HRPQ with mPGIS and PGIC completed last
 - at Month 8 visit: mPGIS, PGIC, HRUQ and HRPQ with mPGIS and PGIC completed last.
- Concomitant treatments recording
- AE recording
- Completion of the paper C-SSRS questionnaire (version for "already enrolled subjects" (see Appendix R) for patients responding to the C-SSRS for the first time during the study, or version "since last study visit" (see Appendix S) for patients for whom the C-SSRS was completed at the previous study visit)

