#### 4.2.11. Baseline Definitions

The baseline will be described in two ways:

- Main Baseline, defined in the Statistical Analysis Plan of the main study and calculated according to first dose of IMP taken during the main Study.
- Second Baseline (named Baseline 2), defined as the last assessment before the first active dose of IMP during the extension study. The baseline 2 will be calculated only for the subjects who are in the placebo arm (actual arm) in the main study.

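### C-SSRS recall answers are counted in the period when the form is first completed, so placebo-phase ideation can be tabulated as treatment emergent and on-drug ideation as follow-up; no Baseline 2 is applied

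*SAP*

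**What the plan says.** **Emergence and worsening.** SAP 4.8.10 calls a woman emergent if she had no ideation or behavior at baseline and is later recorded as "having reported any type of suicidal ideation/behavior at any time post-baseline (including 'Since Study Start' answers". Worsening compares the most severe ideation rating since study start with the baseline rating.

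**Baseline.** This is the screening lifetime history or, from the 'already enrolled' form, the column on the time before study entry, which "will be used as baseline for subjects already randomized at the time of protocol amendment 3 implementation".

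**Who completes the recall form.** SAP 4.8.10 describes it as "for subjects already enrolled in the Extension study, and who were providing answers to the C-SSRS for the first time during the study". The protocol provides for it "for patients responding to the C-SSRS for the first time during the study" at every visit from Month 7 to Month 12 (10.2.1.2 to 10.2.1.5) and at Month 1 and Month 3 ExFU (10.2.2.1 and 10.2.2.2). Month 6 ExFU (10.2.2.3) has only the since-last-visit version.

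**Follow-up.** SAP 4.8.10 ends: "Same analysis will be repeated on the extension follow-up period".

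**Outputs.** SAP Appendix B lists Table 14.4.15.1, "Suicide-related Treatment Emergent Events (C-SSRS) from Month 7 up to Month 12", and Table 14.4.15.2, "Suicide-related Events (C-SSRS) from Month 1 ExFU to Month 6 ExFU".

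**Baseline 2.** SAP 4.2.11 gives main-study placebo subjects a second baseline, "defined as the last assessment before the first active dose of IMP during the extension study". It is used for BMD (4.8.3), laboratory data (4.8.4), vital signs and physical examination (4.8.5), ECG (4.8.6) and TVUS (4.8.8). Section 4.8.10 does not use it.

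**The concern.** The 'already enrolled' form (Protocol Appendix R) has two columns: before study entry, and since study start. Neither isolates the extension. If study start means main-study start, a switcher's recall column combines six months on placebo with whatever linzagolix exposure she has had. The SAP places a positive answer in the period of the visit where the form was completed and gives no rule for dividing the recall.

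The two errors run in opposite directions. In the treatment table, placebo-phase ideation can add to a linzagolix-containing column. In the follow-up table, ideation on linzagolix can appear away from the treatment period.

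The missing Baseline 2 is a separate gap and does not depend on the recall form. A switcher with a clean screening history who develops ideation on placebo, and still reports it at Month 7 on the since-last-visit form, meets the emergence definition on linzagolix.

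This SAP analyses safety only, and a conclusion on suicidality can turn on one or two cases.

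**Working it through.** The plan gives no figure for C-SSRS, so there is none to reproduce. The check is on the rules and on what the recall column spans.

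**Three cases under the rules as written**

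| Case | History | First or relevant form | Counted in |
|---|---|---|---|
| A | Placebo / LGX; ideation in main study only | 'Already enrolled', Months 7 to 12: before entry no, since start yes | 14.4.15.1, emergent |
| B | Any group; ideation on linzagolix only | 'Already enrolled', Month 1 or 3 ExFU: before entry no, since start yes | 14.4.15.2 |
| C | Placebo / LGX; negative lifetime history, ideation starts on placebo and persists | Since-last-visit form, Month 7 | 14.4.15.1, emergent |

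Cases A and B need a first C-SSRS inside the extension. Case C does not.

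In women on the same active drug throughout, a recall answer given up to Month 12 can move an event from the main study to the extension, but it stays on the same drug.

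**Span of the recall column, if study start is main-study Day 1**

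Inputs are the nominal days in Protocol 10.2: extension start Day 169, Month 7 Day 197, Month 9 Day 253, Month 12 Day 337, Month 1 ExFU Day 365, Month 3 ExFU Day 421. The formulas assume treatment continues to Month 12.

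- Recall length at visit day d = d − 1
- Main-study part = 169 − 1 = 168 days
- Extension treatment part = min(d, 337) − 169
- Drug-free part = max(0, d − 337)

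| First form at | Recall days | Main study (placebo for switchers) | Extension treatment | Drug-free |
|---|---|---|---|---|
| Month 7 | 196 | 168 (85.7%) | 28 (14.3%) | 0 |
| Month 9 | 252 | 168 (66.7%) | 84 (33.3%) | 0 |
| Month 12 | 336 | 168 (50.0%) | 168 (50.0%) | 0 |
| Month 1 ExFU | 364 | 168 (46.2%) | 168 (46.2%) | 28 (7.7%) |
| Month 3 ExFU | 420 | 168 (40.0%) | 168 (40.0%) | 84 (20.0%) |

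For a woman on linzagolix throughout, the on-drug part at Month 1 ExFU is (168 + 168)/364 = 92.3%, and at Month 3 ExFU 336/420 = 80.0%.

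**If study start meant extension start.** Case A falls away. Case B remains: recall at Month 1 ExFU is 365 − 169 = 196 days, of which 168 (85.7%) are on drug; at Month 3 ExFU it is 421 − 169 = 252 days, of which 168 (66.7%) are on drug. Case C is unchanged.

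**Weight of one case, for illustration.** Planned enrolment reproduces: 450 × 0.80 = 360 and 360 × 0.80 = 288. Assuming equal continuation across the three main-study arms, each switch group is 288 × 1/3 × 1/2 = 48, and one case is 1/48 = 2.1 percentage points. Actual enrolment was substantially lower (SAP 1.2), so one case weighs more.

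**Month 6.** The text of SAP 4.8.10 summarizes from Month 6, Table 14.4.15.1 starts at Month 7, and SAP 4.2.12 puts by-visit Month 6 assessments in the main study. If Month 6 answers were counted, more placebo time would enter the switchers' treatment table.

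**The case against.** Several points on the other side stand.

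- **Few women may be affected.** C-SSRS is scheduled at Month 6 (Protocol Appendix A), and anyone assessed then uses the since-last-visit form at Month 7. The documents do not show that any woman had her first C-SSRS in the extension. A reader might infer that placebo-phase ideation is generally charged to linzagolix; the text supports only that it can be, under these conditions.
- **The recall answers are partly visible already.** SAP 4.8.10 lists 'Since Study Start' as its own category in the by-time-point summary, and Listing 16.2.9.13 covers individual C-SSRS data. What remains is that the cumulative emergence and worsening counts pool recall with period-specific answers.
- **Labels.** A reader might infer that both tables contradict their titles. The title of Table 14.4.15.2 names visits and does not claim onset off drug, and the Placebo / LGX columns show the placebo phase. Only the treatment-emergent wording of Table 14.4.15.1 is at odds with its possible content.
- **Study start is undefined.** Main-study start fits the rule for women already randomized at the amendment, but it is an inference.
- **Over-counting is cautious.** That is a fair defence for the treatment table. It does not cover Case B, where an on-drug event moves to the follow-up table.

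A reader might also conclude that recall answers should be dropped. For an affected woman the recall column is the only C-SSRS record of that time, so dropping it could hide a signal. The phrase limiting counts to the extension does not settle the matter either: the definition then expressly admits recall answers, and the ideation items have no date field (only actual attempts do; Protocol Appendices R and S).

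**Conclusion.** The concern holds in conditional form. As written, SAP 4.8.10 allows ideation from the placebo phase to be counted as treatment emergent for Placebo / LGX women first assessed at Months 7 to 12, and ideation on linzagolix to be counted in follow-up for women first assessed at Month 1 or Month 3 ExFU. The first part assumes that study start means main-study start; the second holds on either reading. The lack of Baseline 2 is a separate gap that also affects switchers who never used the recall form.

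The number of women affected is not given, so no bias can be estimated. A reader might take 86% or 92% as rates of misattribution. They are shares of nominal recall days and say nothing about how often ideation occurred or was misplaced. The point merits a correction to the SAP; it does not undermine the wider safety analysis.

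**What to change.** 1. Define study start in SAP 4.8.10.
2. In Tables 14.4.15.1 and 14.4.15.2, split emergence and worsening into cases resting on since-last-visit answers within the period and cases resting only on 'Since Study Start' recall. Footnote the span that the recall covers. Remove no case.
3. Keep recall positives from women on linzagolix throughout, reported up to Month 12, as on linzagolix. Label recall positives in the Placebo / LGX groups, and any first reported in follow-up, as period not attributable unless the record dates the event.
4. For main-study placebo subjects with a C-SSRS before the first extension dose, add emergence and worsening relative to Baseline 2, defined as the worst answer before that dose. SAP 4.8.6 already takes the highest prior QTcF as its Baseline 2. Let Month 6 answers contribute to Baseline 2 and not to the Month 7 to 12 count.

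Baseline 2 cannot be derived for a woman whose only recall straddles the first extension dose; item 3 covers her.

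The cost is a few sentences, a few extra table rows and a footnote, with no new data. The downside is that some cases will be shown as unattributable.
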